2.3 Rationale

Patients have been reported to suffer from moderate to severe pain after endodontic treatment for up to seven days, and of those the first 2 days pain is commonly the most severe (1). It has been shown that preoperative pain is the one of the major predictors of postoperative pain (2) which suggests that postoperative pain management becomes even more crucial for patients who report to the clinic with ongoing pain.

Endodontic pain is multifactorial and management of postoperative pain is important in terms of reducing both the peripheral and central components of the associated hyperalgesia through different approaches (26). Different postoperative management strategies that have been suggested including NSAID and/or acetaminophen (7), opioids (8), and corticosteroids (9). LLA has also been suggested for postoperative pain control and has been found to be effective up to 12 hours (11). It has also been hypothesized that with the use of LLA inhibits peripheral barrage from primary afferent neurons after the treatment and thereby significantly inhibit sensitization of second order neurons in the pain pathway that then will lead to reduction or elimination of central sensitization resulting in reduction of postoperative pain, not only during the LLA period but also after the resolution of the anesthesia (13).

However, LLA obviously will lead to longer period of soft tissue numbness. Studies have shown that some patients may not like the longer soft tissue numbness because it may alter orofacial function like eating and speaking and thereby possibly affect their quality of life (11, 12). OHIP-14 is a validated instrument that will be able to capture not only the intensity of pain, but also will be able to determine functional limitation, psychological discomfort, physical, psychological and social disability (22). These findings are significant because although bupivacaine may provide anesthesia up to 7 hours, and better postoperative pain management; it may create functional, psychological and social impairments during the time of anesthesia.

The null hypothesis of this study is that there is no difference between a group of subjects exposed to Bupivacaine, a LLA vs. a group exposed to Lidocaine for dental anesthesia regarding oral quality of life change in subjects with preoperative pain (at least 3/10 on Numerical Rating Scale (NRS)) and diagnosed with a pulpal diagnosis of either symptomatic irreversible pulpitis or pulp necrosis and periapical diagnosis of normal periapical tissues, asymptomatic or symptomatic apical periodontitis who will receive pulpectomy/endodontic debridement on a mandibular molar.

It is well established that one of the major predictors of postoperative pain is the preoperative pain associated with the offending tooth. (2). This fact is the rational why only subjects with symptomatic teeth (with preoperative pain at least 3/10) will be recruited from endodontic services on NRS. Bupivacaine or Lidocaine (chosen randomly) will be administered double blinded prior to the endodontic procedure to

CONFIDENTIAL

anesthetize the pulp and surrounding bone with inferior alveolar nerve block (IANB) in lower molars with a dosage of one cartridge. This is a routine route of administration and dosage applied in routine endodontic practice. If the IANB fails, a second cartridge will be administered, again routinely recommended and done in clinical practice.

Some controversy exists in the literature regarding the success of bupivacaine for pulpal anesthesia during the treatment (15-18) because of methodological differences and different inclusion criteria. Also, delayed onset time may be a disadvantage of bupivacaine although, the onset time has been found comparable to lidocaine and there was no statistically significant difference, in mandibular molar teeth (16). However, because of these controversies in literature, success and onset of LA will be also captured and recorded and analyzed in the study without no additional interventions

2.4 Potential Risks & Benefits

2.4.1 Known Potential Risks

Reactions to bupivacaine hydrochloride and epinephrine injection, are the same as characteristic of those associated with other amide-type LAs such as the control agent in the study; 2% lidocaine with 1:100,000 epinephrine. Subjects who report allergies to LAs or any other component of the LA will be excluded from the study. A major cause of adverse reactions to this group of drugs is excessive plasma levels, which may be due to over dosage, inadvertent intravascular injection or slow metabolic degradation.

Excessive plasma levels of the amide-type LAs cause systemic reactions involving the CNS and the cardiovascular system. The *CNS effects* are characterized by excitation or depression. The first manifestation may be nervousness, dizziness, blurred vision, or tremors, followed by drowsiness, convulsions, unconsciousness, and possibly respiratory arrest. Since excitement may be transient or absent, the first manifestation may be drowsiness, sometimes merging into unconsciousness and respiratory arrest. Other CNS effects may be nausea, vomiting, chills, constriction of the pupils, or tinnitus. The *cardiovascular manifestations* of excessive plasma levels may include depression of the myocardium, blood pressure changes (usually hypotension), and cardiac arrest. *Allergic reactions*, which may be due to hypersensitivity, idiosyncrasy, or diminished tolerance, are characterized by cutaneous lesions (e.g., urticaria), edema, and other manifestations of allergy. Detection of sensitivity by skin testing is of doubtful value. Transient facial swelling and puffiness may occur near the injection site.

Small doses of LAs injected into the head and neck area, as small as nine to eighteen milligrams, may produce adverse reactions similar to systemic toxicity seen with unintentional intravascular injections of larger doses. Confusion, convulsions, respiratory depression, and/or respiratory arrest, cardiovascular stimulation or depression and cardiac arrest have been reported. Reactions resulting in fatalities have occurred on rare occasions. In a few cases, resuscitation has been difficult or impossible despite apparently adequate preparation and appropriate management. These reactions may be due to intra-arterial injection of the LA with retrograde flow to the cerebral circulation. Patients receiving these blocks will have their circulation and respiration monitored and be constantly observed. Resuscitative equipment and personnel for treating adverse reactions will be immediately available. Dosage recommendations should not be exceeded. It is essential that aspiration for blood be done prior to injecting any LA, both the original dose and all subsequent doses, to avoid intravascular injection. However, a negative aspiration does *not* ensure against an intravascular injection. Reactions resulting in fatality have occurred on rare occasions with the use of LAs, even in the absence of a history of hypersensitivity.

The solutions, which contains a vasoconstrictor, should be used with extreme caution for patients whose medical history and physical evaluation suggest the existence of hypertension, arteriosclerotic heart disease, cerebral vascular insufficiency, heart block, thyrotoxicosis and diabetes, etc., as well as patients receiving drugs likely to produce alterations in blood pressure. Only subjects who are ASA I and II are included in the study.

Bupivacaine with epinephrine 1:200,000 or other vasopressors should not be used concomitantly with ergot-type oxytocic drugs, because a severe persistent hypertension may occur. Likewise, solutions of

CONFIDENTIAL

This material is the property of the NYU School of Medicine and Langone Medical Center. Do not disclose or use except as authorized in writing by the study sponsor

bupivacaine containing a vasoconstrictor, such as epinephrine, should be used with extreme caution in patients receiving monoamine oxidase inhibitors (MAOI) or antidepressants of the triptyline or imipramine types, because severe prolonged hypertension may result. Subjects who use these drugs will be excluded from the study.

The solutions also contain sodium metabisulfite, a sulfite that may cause allergic-type reactions including anaphylactic symptoms and life-threatening or less severe asthmatic episodes in certain susceptible people. The overall prevalence is very low. Subjects who have sodium metabisulfite allergies will be excluded from the study.

Any adverse reaction that could be caused by bupivacaine is similar, if not identical, to lidocaine because both have a similar chemical composition, both are amide type LA, and both are commonly and interchangeably used in dental practice (10, 27). With all routine precautions taken, exceeding the recommended plasma level and reaching toxic concentrations thus the occurrences of adverse events are reported to be rare during dental treatments.

When the study agent, bupivacaine HCl 0.5% with epinephrine, is used for dental injections, the long duration of anesthesia (7 hours) could increase the possibility of inadvertent biting trauma to tongue, lips, and buccal mucosa. Subjects will be advised not to chew solid foods or test the anesthetized area by biting or probing until normal sensation has returned. Subjects may have difficulty in eating, drinking, talking for a longer period of time, which might affect them physically and psychosocially. However, postoperative pain may also limit subjects' orofacial functioning and wellbeing, which is eliminated by LLA. Therefore, the information to be gained regarding the overall efficacy of bupivacaine by using OHIP-14 is significant and outweighs the risks involved.

Subjects will be asked to spend time filling out questionnaires before and after treatment. We have limited the amount of questions per document to save the subject time. Subjects can complete these questionnaires alone if preferred, or if the subject feels uncomfortable answering any of the questions, they can tell the study coordinator or the PI. Although there is a minor risk for loss of privacy in this study, confidential data collected for research purposes will be labeled with a unique de-identified study subject number and stored securely.

2.4.2 Known Potential Benefits

There may be no direct benefits to subjects for participating in this research study.

Bupivacaine HCl lasts two to three times longer than lidocaine, in many patients up to 7 hours. This may be beneficial if the treatment duration is longer and it may also help managing postoperative pain (11) that might reduce the analgesic use.

The post-treatment pain monitoring involved in this study may help us to identify subjects needing additional or quicker follow up with their clinical provider than would routinely occur.

3 Objectives and Purpose

This is a double-blind randomized controlled single-site trial. The purpose of this trial is to compare oral health related quality of life change, postoperative pain resolution, and to evaluate pain medication use and duration of anesthesia in subjects with preoperative pain (at least 3/10 on NRS) and diagnosed with a pulpal diagnosis of either symptomatic irreversible pulpitis or pulp necrosis and periapical diagnosis of normal periapical tissues, asymptomatic or symptomatic apical periodontitis who either receive LLA (0.5% bupivacaine with 1:200,000 epinephrine) or LA used as standard of care (2% lidocaine with 1:100,000 epinephrine) for pulpectomy/endodontic debridement at NYU Dentistry Endodontic Clinic.

Bupivacaine is a FDA approved anesthesia, which provides anesthesia up to 7 hours following administration. It is approved for use in dentistry both for infiltration and block anesthesia. We will evaluate

CONFIDENTIAL

This material is the property of the NYU School of Medicine and Langone Medical Center. Do not disclose or use except as authorized in writing by the study sponsor

oral quality of life change in subjects as well as the reported pain resolution and duration of postoperative pain in subjects who will undergo pulpectomy/endodontic debridement for a mandibular molar.

Controversies in literature regarding the success and onset of LA exist. This is why an exploratory objective will capture, record and analyze the success and onset of LA in two study arms in the study without additional interventions.

3.1 Primary Objective

Assess whether pulpectomy/endodontic debridement with 0.5% bupivacaine with 1:200,000 epinephrine (as a LLA) differs with respect to changes from preoperative baseline to postoperative day 1 or day 5 in oral health related quality of life (as measured by OHIP-14 questionnaire), than treatment with 2% Lidocaine with 1:100,000 epinephrine.

3.2 Secondary Objectives

1. Compare the pulpectomy/endodontic debridement treatment of 0.5% bupivacaine with 1:200,000 epinephrine, as a LLA, with pulpectomy/endodontic debridement treatment of with 2% Lidocaine with 1:100,000 epinephrine, as a LLA, with respect to changes in postoperative pain over days 1-5.
2. Compare the pulpectomy/endodontic debridement treatment of 0.5% bupivacaine with 1:200,000 epinephrine, as a LLA, with pulpectomy/endodontic debridement treatment of with 2% Lidocaine with 1:100,000 epinephrine, as a LLA, with respect to duration of pain medication use over days 1-5
3. Compare the pulpectomy/endodontic debridement treatment of 0.5% bupivacaine with 1:200,000 epinephrine, as a LLA, with pulpectomy/endodontic debridement treatment of with 2% Lidocaine with 1:100,000 epinephrine, as a LLA, with respect to duration of anesthesia (numbness) after treatment.

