Endpoints	
Primary Study Endpoint
 
 • Oral health related quality of life OHIP-14 score changes from preoperative to postoperatively on day 1 and day 5. 
Secondary Study Endpoints
 
 • Postoperative pain intensity during 5 days • Number and type of pain medication use • Duration of LA in hours (numbness) after receiving pulpectomy/endodontic debridement 
Exploratory Endpoints
 
 • Cold test results (+/-) • Number of supplemental injections • Duration until adequate lip numbness is obtained (in minutes) • Duration until negative cold response is obtained (in minutes)
Study Duration	The estimated duration of this study is 1 year
Participant Duration	4 weeks ± 10 days (until the second appointment with the subject)
Duration of IP administration	
The duration of administration of either Bupivacaine or Lidocaine as an inferior alveolar nerve block (IANB) lasts up to two minutes.
 
The duration of anesthesia following administration is up to 7 hours for Bupivacaine and up to 4 hours for Lidocaine.

Population	Patients presenting to the NYU Dentistry Department of Endodontics for endodontic care for a symptomatic mandibular molar tooth, aged between 18-85 years, any gender, all demographic and ethnic groups and ASA I or II.
Study Sites	NYU College of Dentistry Department of Endodontics
Number of Participants	We plan to enroll 50 subjects in each group; approximately 100 participants will be enrolled. 20% dropout rate is expected, with an expected 40 subjects in each group.
Description of Study Agent/Procedure	Bupivacaine is an FDA approved anesthetic drug, commercially available (0.5% Bupivacaine with 1:200,000 epinephrine) routinely administered intraorally by IANB.
Reference Therapy	Lidocaine is an FDA approved anesthetic drug, commercially available (2% Lidocaine with 1:100,000 epinephrine) routinely administered intraorally by IANB.
Key Procedures	Preoperative data collection, administration of an IANB (Bupivacaine or Lidocaine), followed by standard of care 1 st visit endodontic procedure; pulpectomy/endodontic debridement. Postoperative data collection during 5 days after treatment.

CONFIDENTIAL

[figure not shown]
This material is the property of the NYU School of Medicine and Langone Medical Center. Do not disclose or use except as authorized in writing by the study sponsor

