4.1.2 Secondary Study Endpoints

- Postoperative pain intensity during 5 days
- Number and type of pain medication use
- Duration of LA in hours (numbness) after receiving pulpectomy/endodontic debridement

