After the adequate lip numbness is gained, another 10 minutes will be waited to achieve pulpal anesthesia; Cold Test – As per standard of care, Endo-Ice (Coltene, USA) will be administered to subjects to determine the success of pulpal This is a routine step in endodontic treatment. A cotton pellet is sprayed with the refrigerant spray and applied the tooth. A painful response will indicate inadequate pulpal anesthesia.

Subjects in each group will also receive a buccal infiltration and IL injection with Lidocaine which is highly recommended for symptomatic teeth. The Cold Test will be repeated to determine anesthesia. The algorithmic chart for anesthetic administration in the supplementary form *Pulpectomy/Endodontic Debridement Method* will be followed as the guideline. Additional supplemental injections will be administered as portrayed in the chart with Lidocaine HCl 2% 1:100,00 in both groups if needed, until pulpal anesthesia is obtained to initiate treatment, without jeopardizing the maximum dose limit for the subject.

Subjects who need supplemental injections more than 2 times will be excluded the study.

4. Intra- and Immediate Post-operative Data Collection:

- Pre-operative data obtained after clinical and radiographic examination which are performed as standard of care, before the treatment procedure, such as cold test response, percussion hypersensitivity, pulpal and periapical diagnosis will be collected by a study investigator by the end of the treatment, together with the intraoperative and immediate postoperative data.
- Intraoperative data such as number of cartridges used, time for adequate anesthesia, additional supplementary anesthesia will be collected.
- Intraoperative pain will be evaluated on a NRS by asking the subject directly after treatment.

5. Remote Data Collection:

Subjects will receive surveys remotely either by e-mail through REDCap, which will ask about their pain intensity reported on an NRS, analgesic medication use and numbness. REDCap surveys will be sent at 6, 12, 24, 48, 72, 96 and 120 hours after treatment. On day 1 and 5, subjects will be assessed by OHIP14.

If subjects do not have access to the Internet, a study team member will call them. Paper questionnaires will also be an option if no other methods are convenient for subjects. If they prefer to fill in the questions and questionnaire on paper, they will be asked to bring them to their second appointment.

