10.2.4 Secondary Analysis

1. For the secondary objective we will compare the efficacy of bupivacaine with that of lidocaine over the postoperative 5 days using mixed models for longitudinal data. The efficacy will be compared in terms of the following measures: postoperative pain resolution,
2. pain medication use,
3. numbness (duration of LA) after receiving endodontic treatment

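### The secondary pain objective does not clearly include the 6 h and 12 h scores, and the mixed model names no time coding, arm-by-time term or deciding contrast

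*Combined protocol and SAP*

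**What the plan says.** - **Objective** (3.2, item 1; repeated in the Protocol Summary): the arms are compared "with respect to changes in postoperative pain over days 1-5". The objective does not say at which hour day 1 begins.
- **Endpoint** (4.1.2): "Postoperative pain intensity during 5 days".
- **Analysis** (10.2.4; repeated in the Protocol Summary): bupivacaine is compared with lidocaine "over the postoperative 5 days using mixed models for longitudinal data". The measure changes name: "The efficacy will be compared in terms of the following measures: postoperative pain resolution". Resolution is not defined. Nothing is said about how time is coded, whether arm interacts with time, which baseline covariate is fixed in advance, or which estimate answers the objective.
- **Data collected** (7.1.1 item 5; same times in 7.2.3): "REDCap surveys will be sent at 6, 12, 24, 48, 72, 96 and 120 hours after treatment".
- **Expected timing of benefit**: the Protocol Summary states "The duration of anesthesia following administration is up to 7 hours for Bupivacaine and up to 4 hours for Lidocaine". Section 2.3 says that long-lasting anesthesia for postoperative pain control "has been found to be effective up to 12 hours". Sections 2.1 and 2.3 also hypothesise that less central sensitization lowers pain after the block has worn off.

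**The concern.** The seven surveys fall into two groups: 6 h and 12 h, close to the drug's action, and 24, 48, 72, 96 and 120 h, which line up one-to-one with days 1 to 5. An analyst who takes the objective literally would model the last five. One who follows the endpoint and analysis wording would model all seven. Both could defend the choice.

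Within either dataset, a mixed model can yield an arm main effect averaged over time, a difference in linear slopes, an arm-by-time test or a contrast at chosen times. These answer different questions. The protocol's two claims about timing need two different contrasts, and the plan assigns none. The pain result could therefore turn on a modelling choice made after the data are seen, and a null result would not say which claim had failed.

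**Working it through.** **1. The plan's own power figure.** Only the OHIP-14 comparison is powered (section 10.1): 40 per arm, difference 9.3, SD 13.3, two-sided 2.5%. The noncentrality is 9.3 / (13.3 × √(2/40)) = 3.13 on 78 df, giving 79.8% power. The stated 80% reproduces. No effect, SD, correlation or power is given for pain, so the rest is illustration.

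**2. Wording side by side.**

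| Place | Window | Outcome name |
|---|---|---|
| 3.2, Protocol Summary objective | days 1-5 | change in postoperative pain |
| 4.1.2, Protocol Summary endpoint | 5 days | pain intensity |
| 10.2.4, Protocol Summary analysis | postoperative 5 days | pain resolution |
| 7.1.1, 7.2.3 | 6 to 120 h, seven scores | NRS pain intensity |

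**3. Assumptions.** True difference 1.5 NRS points at 6 h and 12 h and zero later; SD 2-3 at each time; equal correlation ρ = 0.3-0.7 between times; 40 per arm; two-sided 5%, the default level in 10.2.2.

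**4. Formulas.** The SD of a subject's mean over k times is SD × √((1 + (k−1)ρ)/k). The noncentrality is effect / (that SD × √(2/40)), with power from the noncentral t on 78 df. For the 6-df arm-by-time test with categorical time, a chi-square approximation is used, with noncentrality (40/2) × Σ(dᵢ − d̄)² / (SD²(1−ρ)).

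**5. Middle case, SD 2.5 and ρ 0.5.**
- Mean of 6 h and 12 h: SD 2.5 × √(1.5/2) = 2.17; noncentrality 1.5/(2.17 × 0.2236) = 3.10; power 86%.
- Seven-time average: effect 1.5 × 2/7 = 0.43; SD 2.5 × √(4/7) = 1.89; noncentrality 1.01; power 17%.
- 24-120 h only: effect zero, so the rejection rate is 5%.
- Arm-by-time: Σ(dᵢ − d̄)² = 4.5 − 7 × 0.4286² = 3.21; noncentrality 20 × 3.21/3.125 = 20.6; power 95%.

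**6. If half the effect persists (0.75 points at 24-120 h).** The seven-time effect is (2 × 1.5 + 5 × 0.75)/7 = 0.96, with noncentrality 2.28 and power 62% in the middle case. The 24-120 h average has SD 2.5 × √(3/5) = 1.94, noncentrality 1.73 and power 40%.

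**7. Results.** Ranges are over SD 2-3 and ρ 0.3-0.7.

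| Analysis | Early-only effect: range (middle) | Half persists: range (middle) |
|---|---|---|
| 6 h/12 h mean | 67-98% (86%) | 67-98% (86%) |
| 6-df arm-by-time | 65-100% (95%) | not computed |
| Seven-time average | 11-32% (17%) | 38-92% (62%) |
| 24-120 h average | 5% (5%) | 24-70% (40%) |

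**The case against.** A reader might infer that the early scores are excluded or averaged away, and that the trial will therefore probably report no pain difference. The documents do not support that, for three reasons.

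- **Exclusion is not stated.** The endpoint and analysis wording has no day-1 start. The 6 h and 12 h surveys are listed in one series with the rest. Section 7.2.2 labels the baseline-and-treatment visit as Day 0/Day 1, so the treatment day could itself be counted as day 1.
- **Averaging is not stated.** Section 10.2.4 does not specify an arm main effect. Words such as change and resolution suggest a trajectory, for which arm-by-time is a natural test. Under the same assumptions that test has 65-100% power, and in the middle case it exceeds the early contrast (95% against 86%).
- **The benefit is not placed only at 6-12 h.** Sections 2.1 and 2.3 also expect benefit after the anesthesia resolves and say that the first two days are commonly the worst. A five-day comparison fits that part of the rationale, and the seven-time average does much better if the effect partly persists.

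It can also be said that at 6 h bupivacaine anesthesia may still be active, so an early contrast partly reflects residual anesthesia, and duration of numbness is already a separate secondary endpoint.

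All of this stands, and it limits the point to a gap in specification. It does not close the gap: analyses that the text equally permits range from 5% to 95% power in the middle case. An omnibus arm-by-time test also does not say when, or in which direction, the arms differ.

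**Conclusion.** The concern holds as an ambiguity with a missing specification. The objective's window reads most naturally as 24-120 h and is not aligned with the endpoint, the analysis or the survey schedule. The outcome has three names. No time coding, interaction term or deciding contrast is given, and the two timed claims have no contrast each.

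That wording gap can be seen directly in the documents. The consequence is less certain: every pain power figure rests on an assumed 1.5-point effect, assumed SDs and correlations, equal correlation between times and 40 evaluable subjects per arm. Confidence is medium overall. Because this is a secondary outcome and the primary OHIP-14 comparison is untouched, the change is advisable rather than essential.

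**What to change.** 1. In 3.2 and the Protocol Summary, restate the outcome as postoperative pain intensity (NRS) from 6 h to 120 h. Use that one name in 4.1.2, 10.2.4 and the Protocol Summary.
2. In 10.2.4, specify a linear mixed model of NRS at all seven times with arm, categorical time, arm-by-time and preoperative NRS. Preoperative pain intensity is already collected; enter it as a fixed covariate in this model, not subject to the baseline significance test in 10.2.2.
3. Report the between-arm difference in the mean of 6 h and 12 h, and in the mean of 24-120 h, each with a 95% CI.
4. State which contrast decides the objective, or how the two share the 5% level. The powers above are at 5% and would be lower if it is split.
5. Note that the 6 h score may partly reflect residual anesthesia.

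The cost is a few sentences, with no new data, visits or subjects. The small downside is that the whole-period average becomes a supporting result. The change should be made before unblinded data are seen.
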